12.3.2 Radiotherapy and Surgery

The type of surgery and its outcome will be presented as frequencies and percentages. The time from surgery to neratinib initiation will be presented and calculated as:

- $(Date\ of\ first\ neratinib\ administration - Date\ of\ surgery + 1) / 30.4$

Document: ZZA65950_NEAR_SAP_v2.0

Author: [name]

Version Number: 2.0

Version Date: 22SEP2023

Additionally, the patients with radiotherapy before/after surgery will be described.

12.4 Adverse Events

In this study relevant AEs that occurred between index date and 30 days after Neratinib discontinuation, study entry date or death, whichever occurs first, are collected in the eCRF and will be analyzed. Relevant AEs are defined as all SAEs, AEs leading to dose adaptation or treatment discontinuation, and AEs of interest.

The following are AEs of interest:

- Occurrence of diarrhea
- Gastro-intestinal disorder
- Hepatic disorders
- Cardiac disorders
- Pulmonary disorders
- Pancreatitis
- Reproductive and developmental disorders

SAEs will be identified as those reported as “Serious” on the Adverse Events page of the eCRF, AEs leading to treatment dose change (increase/decrease) or permanent discontinuation of neratinib will be identified from the action taken in the AE details page of the eCRF.

Adverse Events (AEs) will be coded using MedDRA version 24.1.

See Appendix 1 for handling of partial dates for AEs.

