Neratinib (Nerlynx®), an orally available, irreversible tyrosine kinase inhibitor (TKI), was approved by the Food and Drug Administration (FDA) in 2017 and in the European Union (EU) in 2018. In the EU, Neratinib's approved indication is for extended adjuvant therapy of adult patients with early-stage Hormone Receptor-positive (HR+) HER2-overexpressed/amplified breast cancer and who completed prior adjuvant trastuzumab-based therapy less than one year ago. The recommended dose of neratinib is 240 mg (six 40 mg tablets) taken orally once daily, continuously for one year¹⁵. Comparatively, the FDA approved indication applies to a broader profile of patients, where neratinib as a single agent is approved for the extended adjuvant

 Pierre Fabre TEMP CQA 0092 V2.0 Owning site : CORPORATE QA	Template to use for writing Corporate document, except Corporate policy and form, WORD in english	Page 10/29
--	--	------------

therapy of adult patients with early-stage HER2-positive breast cancer, to follow adjuvant trastuzumab-based therapy. Nothing is specified in terms of HR status or the length of prior adjuvant trastuzumab-based therapy.

Certain patients may have received neratinib as per the FDA indication, as part of the EAP in Europe.

Results of the ExteNET trial showed that patients with early-stage HER2+ breast cancer receiving one year of extended adjuvant therapy with oral neratinib (within a year of standard of care adjuvant trastuzumab), had significant improvement in the 2-year iDFS rate compared to placebo (93.9% versus 91.3%, respectively; hazard ratio, 0.67; 95% Confidence Interval (CI), 0.50–0.91; $p = 0.0017$)¹⁶. A 5-year follow-up reported similar results (hazard ratio 0.73; 95% CI 0.57–0.92; $p=0.008$)¹⁷. Furthermore, greater improvement in iDFS was observed in HER2+ patients with HR+ breast cancer¹⁶⁻¹⁸.

An Early access program (EAP) was initiated in Europe in 2017, providing access to neratinib to individual patients following specific criteria outside of a clinical trial. This program is currently ongoing in certain European countries, awaiting product reimbursement. This study will provide real-world data to characterize the profile of patients treated with neratinib, their previous medical history, the conditions for using neratinib and its profile in terms of safety and effectiveness as an extended adjuvant therapy. The profile of patients may be more diverse compared to those enrolled in the ExteNET trial.

Rationale

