4.2.2.3 Patient follow-up

- Initiation of neratinib treatment as an extended adjuvant therapy within the European EAP is the index date for each eligible patient.
- The maximum follow-up duration is until the end of the study observation period (study entry date), up to which all available data will be collected.
- Data will be extracted from existing medical records by the investigator or qualified designee as per standard clinical practice, from baseline till study entry date, death, study withdrawal, or loss to follow-up.
- Data for each patient will be recorded by the investigator or qualified designee in electronic case report forms (eCRF). Following study inclusion, data will be abstracted from the medical charts until study entry date as detailed in section 4.3, and summarized in the data collection schedule (Table 1).

 Pierre Fabre <code>TEMP_CQA_0092_V2.0</code> Owning site : CORPORATE QA	Template to use for writing Corporate document, except Corporate policy and form, WORD in english	
		Page 16/ 29

Table 1: Data collection schedule for eligible patients in the NEAR study

The eligible patients' data from baseline until the end of the study observation period will be collected during data abstraction period (from study entry date to end date of data abstraction).

Data	Baseline Period	Start of Neratinib Treatment	Treatment Phase	End of Treatment (EOT)	Available Tumor / Survival assessment post EOT
Treatment history before neratinib initiation (section 4.3.1)	X				
Patient characteristics at primary diagnosis of breast cancer/neratinib initiation (section 4.3.1)		X			
Neratinib treatment details (section 4.3.2)		X	X	X	
Concomitant treatments with neratinib (section 4.3.2)		X	X	X	
Adverse Events* (section 4.3.2)		X	X	X	
Breast cancer recurrence / Survival status until the end of the study observation period				X	X
Reasons for neratinib discontinuation					X

* For the safety outcomes, only relevant AEs, that occurred during neratinib use (until the end of the study observation period) (section 4.3.2) will be assessed.

 Pierre Fabre TEMP CQA 0092 V2.0 Owning site : CORPORATE QA	Template to use for writing Corporate document, except Corporate policy and form, WORD in english	Page 17 / 29
--	--	--------------

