4.3.2 Secondary outcomes

1. Neratinib treatment patterns will be described, including time to initiation after a trastuzumab based treatment, treatment dose, treatment duration, permanent and temporary discontinuation and reasons for treatment discontinuation or switch at the end of neratinib treatment as an extended adjuvant therapy for early-stage HER2+ breast cancer. All relevant information up to the end of the study observation period will be collected. Additionally, treatment

 Pierre Fabre TEMP CQA 0092 V2.0 Owning site : CORPORATE QA	Template to use for writing Corporate document, except Corporate policy and form, WORD in english	Page 18/ 29
--	--	-------------

persistence, median time to permanent discontinuation and median time to first dosage modification will also be evaluated via Kaplan-Meier estimates.

The following data will be collected to describe treatment patterns during neratinib use as an extended adjuvant therapy:

- End date of preceding trastuzumab treatment
- Initial dosage, Start and end date (if applicable)
- Dosage modifications (if applicable): dates, new dosage, reason for modification
- Neratinib discontinuation: date and reason for permanent or temporary discontinuation, duration of temporary discontinuation, subsequent treatment after discontinuation
- Subsequent treatment(s) upon disease recurrence or treatment discontinuation
- Concomitant endocrine therapy (for HR+ patients): type, start date, stop date
- Others concomitant treatment (if any): type, start date, stop date
- Corrective treatment for relevant AEs

2. Treatment history for breast cancer before neratinib initiation will be described. The following data will be collected:

- Prior anti-cancer drugs/therapies/procedures for breast cancer: type, medication name, start date and stop date
- Type of surgeries and date
- Radiotherapy after surgery (Yes/No): date and area
- Prior neoadjuvant and/or adjuvant anti HER2-directed therapy(ies) (including trastuzumab): type, start date and stop date
- Outcome of neoadjuvant/ treatment (if applicable): pathologic complete response (pCR) or no pCR
- Concomitant endocrine therapy

3. Frequency of relevant AEs during treatment with neratinib as an extended adjuvant therapy will be determined. Relevant AEs will be defined as all SAEs or AEs leading to dose adaptation or treatment discontinuation, and AEs of interest.

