2 INTRODUCTION

This SAP describes the rules and conventions to be used in the presentation and analysis of patients with early-stage Human Epidermal Growth Factor Receptor-2 positive (HER2+) breast cancer, treated with neratinib as an extended adjuvant therapy in the context of the European Early Access Program (EAP). It describes the data to be summarized and analyzed, including specifics of the statistical analyses to be performed.

This SAP is based on protocol version 1.0, dated 23 September 2021.

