7.10 Changes from Protocol

In the eCRF an additional inclusion criterium was considered, i.e., the patient was diagnosed with HER2+ breast cancer. For analysis proposes this additional criterium is considered in the analysis datasets and used in the identification of the FAS.

In the protocol the study entry date was defined as the cut-off date until when the eligible patients' data as obtained from medical charts are abstracted for analysis in the study. Based on a request from Pierre Fabre, the study entry date was assigned in the SAP to the date of first patient in, 05 July 2022, to ensure that all patients have the same cut-off date.

In section 8.2, two additional periods were considered in the time to event analysis, i.e., in protocol the intervals considered were 1, 3, 6, 9 and 12 and for analysis the periods that will be considered are 1, 3, 6, 9, 12, 15 and 18.

The subgroup analysis considered in section 8.4 has been updated from protocol. The nodal status at initial diagnosis and the tumor size at initial diagnosis were removed from the subgroups of interest. The subgroup previous adjuvant or neoadjuvant therapy was defined in the protocol as "Yes/ No" and will be updated to "Neoadjuvant + Post neoadjuvant treatment/ Adjuvant only".

The following subgroups analysis was added: according to EU label status, Concomitant Corrective Antidiarrheal, Concomitant Prophylaxis Antidiarrheal, Initial Dose of Neratinib.

In the protocol the exploratory analysis was planned to be performed only in HR+ patients, it will be analyzed separately for HR+ / HR- patients.

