12 SECONDARY OUTCOMES

12.1 Neratinib Treatment Patterns

Neratinib treatment patterns will be described as frequencies and percentages or summary statistics, as appropriate, for FAS and by subgroup EU label; Pathologic stage; Residual disease after neoadjuvant treatment; Risk profile; Previous adjuvant or neoadjuvant therapy and Prior transtuzumab-based regimen overall and last treatment (Section 8.4).

For duration of neratinib treatment calculations, the date of first and last neratinib administration will be taken from the eCRF “Neratinib Treatment” form, variables “Neratinib Initiation date” and “Definitive discontinuation date” respectively. Interruptions, compliance, and dose changes are not considered for duration of neratinib treatment.

Neratinib treatment initiation details:

- Time from breast cancer diagnosis to neratinib initiation (months), calculated as:
 - $(Date\ of\ first\ neratinib\ administration - Date\ of\ diagnosis + 1) / 30.4$
- Time from completion of adjuvant trastuzumab-based therapy to neratinib initiation (months), calculated as:
 - $(Date\ of\ first\ neratinib\ administration - Date\ of\ completion\ of\ adjuvant\ trastuzumab-based\ therapy + 1) / 30.4$
- Performance status scale used at neratinib initiation: ECOG, Karnofsky, Other
 - If ECOG: 0, 1, 2, 3, 4, Unavailable
 - If Karnofsky: 100, 90, 80, 70, 60, 50, 40, 30, 20, 10, Unavailable and 90-100, 70-80, 50-60, 30-40, 10-20, Unavailable
- Performance status computed ECOG score (based on Table 3): 0, 1, 2, 3, 4, Unavailable
- Duration of neratinib treatment (months), calculated as:
 - For discontinued treatment,
 $(Date\ of\ last\ administration - Date\ of\ first\ administration + 1) / 30.4$

Document: ZZA65950_NEAR_SAP_v2.0

Author: [name]

Version Number: 2.0

Version Date: 22SEP2023

- For ongoing treatment, (*EOB date - Start date + 1*)
- Duration of neratinib treatment (categorized): ≤ 3 months, > 3 months to < 12 months, 12 months, >12 months
- Initial daily dosage (mg)
- Initial daily dose (mg), category: 40mg, 80mg, 120mg, 160mg, 200mg, 240mg, ...; and <240mg, 240mg, >240mg

Treatment modifications (dosage changes):

- Number and percentage of patients with at least one neratinib treatment modification. Percentage computed among FAS.
- Number of temporary modifications by patient
- Temporary modifications per patient category: 1, 2, >2. Percentage computed among FAS patients with at least one neratinib treatment modification.

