12.4.1 Relevant AEs

Relevant AEs will be summarized as number and percentage of subjects experiencing the event and number of events reported. The analysis of all relevant AEs recorded in the eCRF will be presented by the following variables for FAS and by subgroup EU label; Prior trastuzumab-based regimen overall and last treatment:

- Any relevant AE
- Any AEs of special interest
 - by interest type: Occurrence of diarrhea, Gastro-intestinal disorder, Pulmonary disorder, Reproductive and developmental disorder, Hepatic disorder, Cardiac disorder, Pancreatitis
- Any SAEs
 - by SAE type: Death, Life threatening, Hospitalization due to AE – initial or prolonged, Congenital diseases/abnormalities, Disability/ incapacity and Other clinically significant conditions
- By Severity: Grade 1, 2, 3, 4 and 5
- By Action taken: None, Treatment dose increased, Treatment dose decreased, Treatment discontinued, Corrective treatment
- By Outcome: Recovered, Recovered with sequelae, Recovering, Not recovered, Death, Unknown
 - By Causal relationship to neratinib treatment: Reasonable possibility, Not reasonable possibility

If number of patients is large enough, the following analyses will be performed :

- Relevant AEs by SOC and PT for each Severity grade
- Relevant AEs by SOC and PT for each Severity grade by subgroup Prior trastuzumab-based regimen subgroup
- Relevant AEs by SOC and PT for each Severity grade, for patients with treatment discontinuation reason “Patient wish”

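### SAP 12.4 analyses relevant AEs up to 30 days after neratinib stops, the protocol's outcome is AEs during treatment, and SAP 7.10 does not list the change

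*SAP*

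**What the plan says.** **Protocol.** Section 4.3.2 sets the third secondary outcome: "Frequency of relevant AEs during treatment with neratinib as an extended adjuvant therapy will be determined". The footnote to Table 1 (section 4.2.2.3) limits the safety assessment to "only relevant AEs, that occurred during neratinib use (until the end of the study observation period" (the parenthesis closes after these words). In that table the AE row is marked at the start of neratinib, in the treatment phase and at end of treatment. The column for assessments after end of treatment carries no AE mark.

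**SAP.** Section 12.4 covers "relevant AEs that occurred between index date and 30 days after Neratinib discontinuation, study entry date or death, whichever occurs first", and says that these events are both collected in the eCRF and analysed. The study entry date is the common data cut-off, 05 July 2022 (SAP 7.5). On the summary measure, 12.4.1 says: "Relevant AEs will be summarized as number and percentage of subjects experiencing the event and number of events reported". The diarrhea summaries in 12.4.2 use the same measure. Neither section has an on-treatment restriction, a rate per unit of exposure, or a sensitivity analysis without the 30 days.

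**Declared changes.** SAP section 2 names its parent document: "This SAP is based on protocol version 1.0, dated 23 September 2021". Section 7.10 lists departures from it, including small ones; for example, it records that "two additional periods were considered in the time to event analysis". The AE window is not listed.

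**The concern.** The window decides which patients count as having an event, so it is part of the definition of the outcome. Here a secondary outcome defined as on-treatment frequency becomes a frequency over treatment plus up to 30 days off drug, and a reader who relies on 7.10 would not learn of it.

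The added days are also of a different kind. The patient has stopped neratinib, and may have moved to another therapy (SAP 12.1 records a switch after definitive discontinuation). An event in those days need not reflect neratinib. If it shares a row with on-treatment events, the reader of the final report cannot take it out again.

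**Working it through.** The plan states no AE frequency or AE-window figure to reproduce. The check is a comparison of the texts, followed by arithmetic on the added time.

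**Inputs from the documents**
- Added window: 30 days (SAP 12.4). Month length: 30.4 days (SAP 12.1 formulas).
- Labelled course: "taken orally once daily, continuously for one year" (Protocol section 2).
- Duration categories that the SAP expects to fill: "Duration of neratinib treatment (categorized): ≤ 3 months, > 3 months to < 12 months, 12 months, >12 months" (SAP 12.1).
- Last possible index date: 31 December 2020 (SAP 7.1). Cut-off: 05 July 2022 (SAP 7.5).

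**Not in the documents, so assumed.** AE rates on and off drug, and the pattern of stopping times. I take a 12-month on-treatment risk R of 10%, 40% or 80%, and a hazard after stopping that is a fraction f = 0, 0.25 or 1 of the on-treatment hazard.

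**Step 1: the two windows.** The protocol runs from index date to the end of neratinib use, capped at the end of observation. The SAP runs from index date to the earliest of discontinuation plus 30 days, cut-off, or death. They differ for every patient who stops and is still observed afterwards.

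**Step 2: does the cut-off shorten the extra window?** A patient indexed on 31 December 2020 has 551 days to cut-off. A 365-day course ends on 31 December 2021, and 30 more days end on 30 January 2022, before 05 July 2022. So early stoppers and one-year completers get the same full 30 days, unless death or loss to follow-up comes first.

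**Step 3: added time relative to exposure,** 30/(30.4 × m) for a stop at m months:
- 1 month: 30/30.4 = 99%
- 3 months: 30/91.2 = 33%
- 6 months: 30/182.4 = 16%
- 12 months: 30/364.8 = 8%

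**Step 4: effect on the percentage with at least one event.** With constant hazard h = −ln(1−R)/365 per day and T = 30.4 × m, the added share is exp(−hT) − exp(−h(T + 30f)). For R = 40%, h = 0.5108/365 = 0.0014. At 1 month with f = 1 the percentage goes from 4.17% to 8.11%, or +3.9 points. For changing hazards I use a Weibull curve, exp(−(t/s)^k), with s set to give R at 365 days and the hazard continuing after the stop. All rows treat stopping as unrelated to AEs.

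| Assumption | 1 mo | 3 mo | 6 mo | 12 mo |
|---|---|---|---|---|
| R 10%, constant, f = 1 | +0.85 | +0.84 | +0.82 | +0.78 |
| R 40%, constant, f = 1 | +3.9 | +3.6 | +3.2 | +2.5 |
| R 80%, constant, f = 1 | +10.8 | +8.3 | +5.5 | +2.5 |
| R 40%, constant, f = 0.25 | +1.0 | +0.9 | +0.8 | +0.6 |
| Any R, f = 0 | 0 | 0 | 0 | 0 |
| R 40%, falling (k = 0.5) | +5.1 | +3.0 | +2.0 | +1.2 |
| R 40%, rising (k = 2) | +1.0 | +2.3 | +3.9 | +5.0 |

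The size and the order across stopping times both depend on assumptions that the documents cannot settle.

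**Step 5: which rows can move.** An AE that led to discontinuation is itself a relevant AE, so a patient who stopped for one is already counted under any relevant AE, and one who stopped for diarrhea is already counted under diarrhea. The extra days cannot raise those patient percentages for them. AEs leading to dose change or discontinuation should not newly arise after the drug is stopped. What can rise is the percentage with an SAE or AE of interest among patients not yet counted in that row, and the number of events.

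**The case against.** The best defence is that the protocol never fixes an operational end for the on-treatment period. Its footnote is loosely worded and its end-of-treatment time point is undefined, so SAP 12.4 can be read as making the outcome operational, and it does so openly. The looseness is real. But the footnote's parenthesis reads most naturally as a cap on the on-drug period, and on the wider reading the window would run to 05 July 2022. Neither reading gives 30 days.

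The outcomes are descriptive, and no test or decision rests on the AE percentages. The SAP's own precision at 120 patients is ±5.4 to ±9 points for proportions of 10% to 50%. This limits the practical weight of the point, but does not change what the tables measure. The breakdown by causal relationship helps a little, but attribution is not timing.

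The table layouts are in shells supplied with the SAP (section 9) and not among the documents reviewed. So the point holds for the tables as the SAP text describes them.

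A reader might go further and infer that AE frequencies rise most for early stoppers, and so distort the tables by prior regimen. The documents do not support this. The added time is the same 30 days for early stoppers and completers, and is larger for early stoppers only relative to exposure. The inference needs an off-drug event rate close to the on-drug rate. It vanishes if events cease with the drug, reverses under a rising hazard, and ignores patients already counted because an AE made them stop. No stopping rates by regimen are given. Even granting a constant 0.05 events per month on and off drug, the added share is exp(−0.05 × 12) × 0.0481 = 2.6 points at 12 months and exp(−0.05) × 0.0481 = 4.6 points at 1 month, where 0.0481 = 1 − exp(−0.05 × 30/30.4). If 30% of one group and 10% of another stopped at 1 month and the rest at 12 (an assumption), the difference between groups would shift by 0.2 × (4.6 − 2.6) = 0.4 points. At 0.10 per month it would be 0.2 × (8.5 − 2.8) = 1.1 points.

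Finally, an on-treatment flag is imperfect: it includes temporary interruptions, and Appendix 1 bends it. An AE start with a missing day moves to the first of the month and a discontinuation date to the last, so an AE after stopping in the same month would be classed as on treatment. Both objections stand, and the fix has to meet them.

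**Conclusion.** The mismatch is in the text and needs no assumption: the protocol's outcome is on-treatment, the SAP's window adds up to 30 days, 7.10 is silent, and no SAP text separates the periods. The AE frequencies as described answer a different question from the protocol's.

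The extra observed time is 8% of a 12-month course, 33% of 3 months and 99% of 1 month. The change in AE percentages cannot be computed from the documents. It is nil if events end with the drug and probably modest otherwise; the larger figures in the table need a high event rate that continues unchanged off drug. A greater effect in early stoppers is not established.

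A 30-day safety window can be defended in its own right, and nothing here calls for its removal. The plan should correct this before the tables are produced, because a secondary outcome's definition has changed without being declared and the repair is cheap.

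**What to change.** - **SAP 12.4:** derive an on-treatment flag, with onset from index date to definitive discontinuation date (or end of observation if treatment is ongoing). Report the protocol's secondary AE frequencies, including the diarrhea summaries, with it.
- **Separate row:** show events with onset on days 1 to 30 after discontinuation on their own line, and label any combined summary as on treatment or within 30 days.
- **Partial dates:** list AEs whose period cannot be determined because the AE start or the discontinuation date is partial, so that Appendix 1 imputation does not silently class them as on treatment.
- **Interruptions:** state that temporary interruptions count as on treatment. This agrees with SAP 12.1, which ignores interruptions when it computes treatment duration.
- **SAP 7.10:** add the 30-day extension, with its reason.

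The AE start and definitive discontinuation dates are already collected, so no new data are needed. The cost is one derived flag, one extra row or table, a short listing and a few sentences of SAP text.
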